# C. Statistical Power

Power calculations were conducted with the statistical software package STATA. For repeated measures ANCOVA models, we assumed high correlation between follow-up assessments for the outcome of interest. Power was calculated for our study with 1 prerandomization baseline assessment and 12 follow-up assessments. For Hypotheses 1, comparing baseline to follow-up measures within group, the power to detect differences in YMRS or CDRS scores of 5 points (SD=10 points) is 0.86 with alpha set at 0.05. For differences in YMRS or CDRS scores of 7.5 points, power increases to 99%. For hypothesis 2 and Exploratory Hypothesis 3, testing differences between groups, the power to detect differences in YMRS or CDRS scores of 5 points (SD=10 points) is 0.93 with alpha set at 0.05 and 0.81 with alpha set at 0.01.

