We will enroll 90 subjects to allow for randomization of 30 subjects into each treatment arm of the study. The subject's first visit to the office consists of a meeting with a study clinician who explains the study, obtains informed consent, and administers an abbreviated form of the structured diagnostic assessment (45-90 minutes). After the evaluation with the study clinician, the subjects will undergo a neuropsychological assessment (45-60 minutes).

We anticipate that subjects may enter this trial following completion of/withdrawal from other Bipolar Disorder protocols in our office, and that there may be procedural overlap. So as to not burden subjects/parents/guardians with redundant time commitments, we will use the following data if previously collected:

- **Diagnostic Data:** If a subject has completed an evaluation with one of the study clinicians and/or the structured assessment within the previous 12 months prior to entrance into this study, they will not be asked to repeat any overlapping diagnostic procedures. However, the study clinician will review the interval time period to assess for clinically significant medical or psychiatric history, to ensure that the subject meets appropriate study entrance criteria.
- **Cognitive and Neuropsychological Testing:** If the subset of scales assessing intelligence (WASI or KBIT-2 for 5 year-olds) and cognitive functioning (select WISC tasks or WPPSI-III tasks for 5 year-olds) in the neuropsychological battery

have been completed within 12 months prior to entrance into this study, subjects will not be asked to repeat these procedures at screening/baseline.

• Screening Rating Scales: If a parent has completed the Child Behavior Checklist (CBCL), Social Responsiveness Scale (SRS), or the Behavior Rating Inventory of Executive Function – Parent Form (BRIEF) within the past six months as part of one of our screening protocols, we will not ask the parent/guardian to repeat these scales at screening/baseline.

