# Screening Visit

Before any participant can start the study, the study clinician will discuss the details of the study with the participant and his/her parent/guardian. Before starting the screening process, the study clinician will obtain informed consent from the parent or guardian and assent from the child subject. Assent will be obtained, in writing, from each child age 7-12 years who, in the opinion of the Investigator, is capable of providing assent based on their age, maturity, and psychological state. When assent is not obtained, the Investigator will document his/her rationale in the research records.

After the consent/assent form is signed, we will do the following:

- Review medical and health questions with the participant and their parents/guardians. (For example, "Does your child have a history of any medical conditions such as diabetes or hypertension?")
- Conduct a brief demographic interview. This interview will be used to estimate socioeconomic status, as well as collect information about any educational accommodations, and past head injuries and trauma.
- Obtain psychiatric history and administer YMRS, the CDRS, the HAM-D, the C-SSRS, and the K-SADS-E mania and depression modules to determine that subject meets the diagnostic criteria of a current DSM-IV bipolar spectrum disorder (mixed, manic, or hypomanic) and has an YMRS score of ≥ 20 and < 40.

All exclusionary and inclusionary criteria will be reviewed. Appropriate patients will undergo:

- An assessment battery (CBCL, SAICA, FES)
- Cognitive evaluation [IQ and cognitive function (subtests of WISC-IV, WPPSI-III, or KBIT-2)]

- Select WPPSI-III subtests will be used in the place of the WISC-IV processing speed subtest for children younger than 6 years.
- The KBIT-2 will be used in the place of the WISC-IV to assess IQ in children younger than 6 years.
- Physical exam
- Tanner staging exam (clinician-administered to parent or subject, clinician exam with subject, or the option to refuse)
- Vital Signs (blood pressure, pulse, height, weight, temperature)

The above may take place over two visits over the course of three weeks, if necessary. All are to be completed prior to the Baseline Visit. Any subjects requiring medication washout must be tapered off this medication prior to Baseline Visit as indicated in the washout section. Patients who do not meet all the criteria for enrollment after these assessments will be discontinued.

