# Baseline (Week 0)

Subjects must continue to meet all inclusionary and exclusionary criteria at this visit

- Study clinician will administer Baseline Scales
- Vital signs (blood pressure, pulse, height, weight, temperature)
- Subjects will receive study medication as indicated by a blinded randomization schedule

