# Efficacy Measures

The primary efficacy measures are the mean change from baseline to endpoint in the Young Mania Rating Scale (YMRS) total score and the Children's Depression Rating Scale (CDRS). These will be administered by the clinician at Screening Visit, Baseline Visit, at each of the weekly visits and endpoint.

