# 1. Young Mania Rating Scale (YMRS)

- The YMRS (Young, 1978) consists of 11 items rated on a scale from 0 (symptom not present) to 4 (symptom extremely severe).
- Items 5, 6, 8, and 9 are rated on a scale from 0 (symptom not present) to 8 (symptom extremely severe). These items assess irritability, speech, content and disruptive/aggressive behavior) and are given extra weight in the overall score.
- The YMRS score ranges from 0-60. Questions are asked about the last week. This scale is generally accepted as the main outcome measure in studies of pediatric bipolar disorder and is linked directly to the core symptoms of mania.

Collected at the Screening Visit, Baseline Visit (only subjects with a YMRS score of 20 or greater, but not above 40, are included), at each of the weekly visits and at endpoint to assess the impact of treatment on manic symptoms.

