# 2. Children's Depression Rating Scale (CDRS)

- The CDRS (Poznanski, 1985) is modeled after the Hamilton Depression Rating Scale for adults, but includes questions relevant to youth, such as questions about school, family and peer functioning.
- This is a clinician-rated instrument with 17 items scored on a 1 to 5 or 1 to 7 scale. A rating of 1 indicates normal, thus the minimum score is 17. The maximum score is 113. Scores of 20-30 suggest borderline depression. Scores of 40-60 indicate moderate depression.
- This scale is generally accepted as the main outcome in studies assessing childhood depression and is linked directly to the core symptoms of depression.
- Collected at the Screening Visit, Baseline Visit, at each of the weekly visits and at endpoint.

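### Both primary scales are scored twice before treatment, but the plan never says that the screening score enters the between-arm models: a missed efficiency, not an error

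*Combined protocol and SAP*

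**What the plan says.** Efficacy Measures (section 8) names the YMRS and CDRS as the primary measures and gives their timing: "These will be administered by the clinician at Screening Visit, Baseline Visit, at each of the weekly visits and endpoint". The CDRS entry repeats it: "Collected at the Screening Visit, Baseline Visit, at each of the weekly visits and at endpoint". The YMRS entry and Table 1 agree.

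Both ratings precede treatment. Of the screening procedures, the Screening Visit text says: "All are to be completed prior to the Baseline Visit". Treatment starts at Baseline (Week 0): "Subjects will receive study medication as indicated by a blinded randomization schedule". The Design section lists data that may be carried over from other protocols, and neither scale is named there.

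Three places bear on how the scores are used:

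- Efficacy Measures defines the outcome as change measured from baseline.
- Hypothesis Testing (section 9, part B) sets up two between-arm repeated measures ANCOVA models for Hypothesis 2, each monotherapy against the combination, and names no covariate.
- Statistical Power (section 9, part C) states: "Power was calculated for our study with 1 prerandomization baseline assessment and 12 follow-up assessments".

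The only use described for the screening score is to establish eligibility.

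**The concern.** Hypothesis 2 rests on two comparisons of 30 children against 30. A second score on the same scale, taken before allocation, can remove residual variance without another visit, rating or child, and adjusting for it cannot bias a randomised comparison. The plan collects that score and then appears to leave it aside.

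The silence of Hypothesis Testing matters too. Two pre-treatment scores will exist, and the text does not fix which of them the ANCOVA adjusts for. That choice should be settled before any outcome data are seen.

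**Working it through.** **Inputs from the document.** Difference 5 points, SD 10, 30 per arm, 12 follow-ups, one pre-randomisation score; stated between-arm power 0.93 at alpha 0.05 and 0.81 at alpha 0.01. For the within-arm test (Hypothesis 1), stated power is 0.86 at 5 points and 99% at 7.5 points. Follow-up correlation is described only as high; no correlation is given as a number.

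**Assumed.** Two-sided tests, normal approximation, treatment contrast on the mean of the 12 follow-ups. Let r1 be the correlation between follow-ups, rb of baseline with follow-up, rs of screening with follow-up, and r0 of screening with baseline.

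**Formulas.**

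- One pre-score: f = (1 + 11·r1)/12 − rb²
- Two pre-scores: f = (1 + 11·r1)/12 − (rb² + rs² − 2·rb·rs·r0)/(1 − r0²). When rs = rb, the subtracted term is 2·rb²/(1 + r0).
- SE = 10·√(2f/30); power = Φ(5/SE − z), with z = 1.960 or 2.576.

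**Step 1: reproduce the plan's figures.** With r1 = 0.80, (1 + 8.8)/12 = 0.8167. The within-arm SE is 10·√(0.8167/30) = 1.650, giving power 0.858 at 5 points and 0.995 at 7.5, in line with the plan. For the between-arm test, rb = 0.71 gives f = 0.8167 − 0.5041 = 0.313, SE = 1.444, and power 0.934 and 0.813. The stated 0.93 and 0.81 are therefore consistent with one baseline score. These correlations are back-solved, and other pairs fit too (r1/rb of 0.70/0.64 or 0.90/0.77).

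**Step 2: an illustrative case.** Take r1 = 0.7, rb = 0.5, r0 = 0.6. Then (1 + 7.7)/12 = 0.725, and with one pre-score f = 0.725 − 0.25 = 0.475, power 0.80. Adding screening:

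| rs | Subtracted term | f | Variance cut | Power, alpha 0.05 |
|---|---|---|---|---|
| 0.50 | (0.25 + 0.25 − 0.30)/0.64 = 0.3125 | 0.4125 | 13% | 0.85 |
| 0.45 | (0.25 + 0.2025 − 0.27)/0.64 = 0.2852 | 0.4398 | 7% | 0.83 |
| 0.40 | (0.25 + 0.16 − 0.24)/0.64 = 0.2656 | 0.4594 | 3% | 0.815 |
| 0.30 | (0.25 + 0.09 − 0.18)/0.64 = 0.2500 | 0.4750 | 0% | 0.80 |

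The last row is rs = r0·rb = 0.6 × 0.5, where screening adds nothing once baseline is known. This case starts from power 0.80, not the plan's 0.93, so it shows the proportional gain only.

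**Step 3: the same check from the plan's own power.** The stated 0.93 and 0.81 imply f of about 0.318 and 0.314; take 0.316. With r1 = 0.80, rb² = 0.8167 − 0.316 = 0.5007, so rb = 0.708.

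- rs = rb, r0 = 0.80: f = 0.8167 − 1.0013/1.8 = 0.260, an 18% cut; power 0.967 and 0.889.
- rs = rb, r0 = 0.70 or 0.90: power 0.982 and 0.931, or 0.949 and 0.847.
- rs lower than rb by 0.05, r0 = 0.80: f = 0.293; power 0.947 and 0.842.
- rs = r0·rb: f stays at 0.316; power 0.931 and 0.808, no gain.

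**Step 4: where the gain should be smaller.** The 20–40 YMRS entry window must be met at Screening and again at Baseline. Under a linear model, selecting on the two pre-scores leaves their regression slopes and the residual variance unchanged. It does narrow the spread of screening scores at a given baseline, so the screening score explains less. The CDRS has no such window. Separately, "Any subjects requiring medication washout must be tapered off this medication prior to Baseline Visit as indicated in the washout section", so some screening ratings may be made on a different drug regimen. Screening can also take up to three weeks. Both would tend to pull rs below rb.

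**The case against.** One baseline score is a conventional and valid ANCOVA design, and omitting a second makes the power figure conservative rather than optimistic. That stands: no conclusion becomes invalid if the plan is left as it is.

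A reader might infer that the plan excludes the screening score from the tests. The document does not say so. The count of one appears in a power calculation, and the analysis text names no covariate, so the score is neither included nor ruled out. Non-use is an inference from the power text, the outcome definition and that silence.

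A reader might also take 13% as the expected gain. It requires screening to predict follow-up as well as baseline does, which the taper and the earlier timing make doubtful. The lower rows of the table are equally compatible with the document.

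Finally, the gain depends on what is tested. If the comparison of change over time is read as a group-by-time interaction, a covariate that is constant over time and entered as a main effect does not reduce the within-child error in data completed by carrying observations forward. The variance formula applies to a treatment contrast on follow-up scores. This also stands, and the fix has to name that contrast.

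**Conclusion.** The point holds as a low-cost improvement. Two pre-treatment scores exist on each primary scale, the power calculation counts one, and nothing assigns the screening score to the between-arm models. The stated power is not inflated by this and needs no correction on this account.

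The size is uncertain. In the illustrative case the residual variance cut runs from 13% through 7% and 3% to zero, depending only on how well screening predicts follow-up. All the correlations are assumed. The gain is likely smaller for the YMRS and for children tapered between the two visits.

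A reader might conclude that the power section should be restated with two pre-randomisation scores. The document does not support that. Under the equal-correlation formula, with screening–baseline correlations of 0.7 to 0.9, stated power at alpha 0.05 would rise from 0.93 to about 0.95–0.98 on correlations that appear nowhere in the plan. That could overstate power, most clearly for the YMRS.

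**What to change.** In Hypothesis Testing, state that each between-arm repeated measures ANCOVA adjusts for both the Baseline and the Screening score of the scale being analysed, as two separate covariates, for the treatment contrast on follow-up scores. Separate terms, rather than an average, let the model give less weight to a screening score that predicts less well, for example one taken before a taper.

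Leave the power calculation on one baseline score and describe it as conservative in that respect. Do not change the count to two.

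The cost is one sentence and one model degree of freedom, in comparisons of about 60 children. No visit, rating or child is added.

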# 9. SAFETY

Consistent with good clinical practice, safety will be monitored by each subject's study clinician at each study visit. This clinician will be available 24 hours a day by page. The Principal Investigator will supervise all study activities including ratings, reported adverse events, and vital signs. Subjects will be monitored for adverse events at each visit and adverse events will be recorded on an Adverse Events Form. Treatment-emergent adverse events will be monitored through changes in vital signs. All adverse events will be reported according to PHRC guidelines. Blood pressure, pulse, height, weight, and temperature will be recorded at each visit. Poor response to treatment will be measured by a CGI-bipolar score that is 2 points higher (more severe) than baseline for 2 weeks in a row or a YMRS score that is 30% higher than baseline for 2 weeks in a row, which may lead to drop from the study as determined by the clinician. Subjects with individual YMRS item scores of 8 on Item #8 (Content), or scores greater than 6 on Disruptive-Aggressive Behavior for 2 weeks in a row will be dropped from the study. In addition, drop from study will occur at clinician discretion for worsening of clinical course, noncompliance with treatment or inability to tolerate study treatment. Finally, the Columbia Suicide Severity Rating Scale (C-SSRS) will be administered weekly to assess initial and emergent suicidality in subjects. Subjects with scores of 4 or higher on the C-SSRS will be dropped from the study.

# **10. CONFIDENTIALITY**

All research-related records, initiated as a result of a subject's participation in this study that reveal the subject's identity, will remain confidential except as may be required by law. Subjects will only be contacted regarding future studies if they indicate that they are interested in being contacted by initialing in the specific section of the consent form.

# **11. MONITORING AND QUALITY ASSURANCE**

The Data Safety Monitoring Committee for this study will be made up of two child psychiatrists. One of the child psychiatrists will be from a different institution, specifically the Children's Hospital Medical Center (a Harvard, but non-Partner's Healthcare affiliated institution). None of the members of the DSMC will be affiliated with the study. The DSMC will meet upon enrollment of the first subject and annually thereafter during the study. The DSMC will meet to discuss adherence to the protocol and

to monitor subject participation (e.g. tolerance to medication, drop-out rates, etc.), the risk-benefit ratio, and all Adverse Events throughout the course of the study. In addition to the IRB, the Chairman of the DSMC will be informed of any serious adverse events occurring during the trial. If at any time during the study more than 10% of the patients within any arm of the study have had a serious adverse event, the study will be stopped. The primary concern of the investigators of this study is the safety of the subjects.

# **12. RISKS AND DISCOMFORTS**

Potential side effects are few and will be monitored for throughout the research study. Consent forms will clearly list potential medication side effects. Since they are natural products, it appears that the omega-3 fatty acids and inositol have a low potential for unwanted side effects or negative effects on the child's growth and development. It should also be noted that no important toxic effects have been reported in previous use in humans and animals.

# **Omega-3** Fatty Acids

The treatment omega-3 fatty acids has been used and studied in pediatric populations with few side effects. The most common side effects reported with use of omega-3 fatty acids are upset stomach and complaints of a fishy taste. Other side effects include nausea, skin rashes, decreased platelet aggregation, bleeding tendencies, and increased restlessness.

#### Inositol

Inositol is a safe, natural diet supplement with emerging evidence of utility in psychiatric populations. The most common side effects include mild increases in glucose, flatus, nausea, sleepiness and insomnia, dizziness, headache, and diarrhea.

#### **Other Adverse Events**

Problems and side effects not listed above and not known at this time could occur. Subjects will be told of any changes in the way the study will be done and any newly discovered risks to which they may be exposed.

Answering detailed questionnaires may create a mild degree of inconvenience or emotional upset for the subjects. Interviewers will be trained to support the subjects who raise such concerns, and the PI will be available to respond to any concerns or to answer other questions about the study (available by pager 24 hours per day). All of the information about participants will be treated confidentially. Subjects may refuse to answer any of these questions.

Having treated hundreds of bipolar patients, we are aware that this is a group of very highly disturbed children at risk for psychosis, suicide and disruption in the family. Although it is unlikely that these risks will be exacerbated by the protocol, we will be

vigilant regarding the potential for patient decompensation or dangerousness to self or others. In the execution of research protocols, our primary concern is always the safety of the research participant. Given the especially unstable nature of bipolar patients, we will be available to the study staff and to handle clinical emergencies with patients and their families. The PI has a beeper and is available for emergencies 24 hours per day. The Massachusetts General Hospital has an active and well-staffed psychiatric emergency service that will be available to subjects if needed. This study has clearly defined exit criteria to ensure the safety of participants.

## **Protection Against Risk**

Subjects' confidentiality will be protected throughout the study. Information about subjects and their families will be stored in research files identified only by a code. The code key connecting the participant's names to identifying information will be kept in a separate, secure location. Data in databases is similarly identified only by coded ID number and is password-protected. Data will not leave our institution in any form that would identify individual subjects or families. The information collected in our assessments and treatment outcome rating scales will not become part of the individual's hospital medical record. In the case that serious psychopathology (suicidality, homocidality, psychosis) is uncovered in the course of the research study, the Principal Investigator or appointed proxy will be immediately contacted by the clinician. All efforts will be made to alert parents of the child subject and, if necessary, treating clinicians, of the circumstances to enable the subject to secure appropriate treatment. If needed, emergency evaluation and referral will be available through coverage by the clinician-investigators on this study and through the Acute Psychiatry Service (APS) at the MGH. The APS is a well staffed 24 hour/7 day per week emergency service for psychiatric emergencies. Subjects who do not respond to the study treatments will be dropped from the study using clear drop criteria ("patients may drop at any time due to patient preference, physician decision, need for psychiatric hospitalization or a poor response to treatment. Poor response to treatment leading to drop from the study will be measured by a CGI-mania score that is 2 points lower (more severe) than baseline for more than 2 weeks in a row, a YMRS score that is 30% higher than baseline for more than 2 weeks in a row"), or a C-SSRS score of 4 or higher.

# **13. POTENTIAL BENEFITS**

# To the Subject

The study will offer rapid access to treatment and provide subjects with a free detailed psychiatric and cognitive evaluation. Subjects will be provided with potentially useful treatments which have low risks associated with them, as the treatments are natural elements of the human diet.

